3.4 Primary Safety Endpoints

The safety and tolerability of consolidation Pembrolizumab after concurrent chemotherapy and proton reirradiation will be evaluated. Clinical assessment and laboratory evaluation of Adverse Events and Dose Limiting Toxicities will be done according to the CTCAE, version 5.0 of the NCI Cancer Therapy Evaluation Program (CTEP).

4 Subject Selection and Withdrawal

4.1 Inclusion Criteria

1. Histologic or cytologic diagnosis of NSCLC who have received previous intrathoracic radiation therapy with definitive intent and have a tumor recurrence in or near the prior irradiation fields.

Phase II Pembrolizumab Reirradiation

Re-biopsy of the recurrence is not required and is left to the discretion of the treating physician, although every effort should be made to confirm recurrence pathologically.

2. Eastern Cooperative Oncology Group (ECOG) performance status of 0-1
3. Age 18 or greater
4. Patients with prior invasive malignancies are allowed, provided they have been treated with definitive intent and have no evidence of active disease requiring treatment in the past 2 years.
5. Patients must be capable of giving informed consent and be willing and able to comply with schedule.
6. Serum total bilirubin \leq 1.5 X upper limit of normal (ULN) OR Direct bilirubin \leq ULN for subjects with total bilirubin levels $>$ 1.5 ULN prior to Pembrolizumab treatment.
7. Platelets $>100,000$ cells/mm³ and ANC $\geq 1,250$ cells/mm³ prior to Pembrolizumab treatment.
8. Creatinine \leq 1.5 X ULN OR measured or calculated creatinine clearance ≥ 50 mL/min for subject with creatinine levels $>$ 1.5 X institutional ULN. (GFR can also be used in place of creatinine or CrCl) prior to Pembrolizumab treatment
9. Clinical target volume (CTV) size must be <250 cc, no more than 74 Gy of prior radiation in 2 Gy fractions previously administered.

4.2 Exclusion Criteria

1. Allergy to Pembrolizumab or related compounds
2. History of symptomatic CTCAEv5 grade ≥ 3 pneumonitis following the initial course of definitive radiation therapy
3. History of symptomatic idiopathic pulmonary fibrosis or interstitial lung disease
4. Use of continuous oxygen
5. Diagnosis of immunodeficiency or exposure to systemic steroid therapy or any other form of immunosuppressive therapy within 7 days prior to the first dose of trial treatment. (Nasal or oral inhalers are permissible).
6. Active autoimmune disease requiring systemic treatment within the past 3 months or a documented history of clinically severe autoimmune disease, or a syndrome that requires systemic steroids or immunosuppressive agents. Subjects with vitiligo or resolved childhood asthma/atopy are an exception to this rule. Subjects that require intermittent use of bronchodilators or local steroid injections are not excluded from the study. Subjects with hypothyroidism stable on hormone replacement or Sjorgen's syndrome are not excluded from the study.
7. History of allogenic tissue or solid organ transplant
8. Prior immunotherapy less than 30 days from the planned start of reirradiation
9. Patients with known extrathoracic metastases, including brain metastases, or known malignant pleural or pericardial effusion
10. Prior radiation treatment less than 6 months from the planned start of reirradiation of any part of the intended treatment volume
11. Pregnant or breast-feeding patients. Men and women of reproductive potential may not participate in this study unless they have agreed to use an effective contraceptive method while in this study.
12. Known history of Human Immunodeficiency Virus (HIV) (HIV 1/2 antibodies).
13. Known active Hepatitis B (e.g., HBsAg positive or HBV DNA detectable) or Hepatitis C (e.g., HCV RNA [qualitative] is detected).

4.3 Subject Recruitment and Screening

Subjects will be recruited for this study from the clinical practices of the Abramson Cancer Center at the University of Pennsylvania and Penn Presbyterian Medical Center. Subjects will be required to give written informed consent to participate in the study before any screening tests or evaluations are conducted that are not part of standard care.

4.4 Early Withdrawal of Subjects

4.4.1 When and How to Withdraw Subjects

Subjects who do not complete the study protocol will be considered to have prematurely discontinued the study. The reasons for premature discontinuation (for example, voluntary withdrawal, toxicity, death) must be recorded on the case report form (CRF). Final study evaluations will be completed at the time of discontinuation. Reasons for withdrawal include, but are not limited to, the following:

1. Inter-current illness that would, in the judgment of the investigator, affect assessments of clinical status to a significant degree or require discontinuation of study drugs;
2. Unacceptable toxicity: Patients will be followed until resolution or stabilization;
3. Disease progression;
4. Withdrawal of patient consent;
5. Patient opting out of further treatment in the absence of progressive disease or significant comorbidity but still willing to have follow up regarding disease status;
6. Treatment delay greater than four weeks beyond the schedule for any toxicity
7. Non- compliance with study procedures that cannot be resolved;
8. Major protocol violations, including, but not limited to:
 1. failure to meet inclusion/exclusion criteria;
 2. failure to complete evaluations as required by protocol;
 3. use of concomitant therapies other than specified above.

The reason(s) for withdrawal should be noted in the case report form and in the patient's medical record. Standard supportive therapy should be maintained for subjects withdrawn from active treatment. Long-term follow-up data, including survival and progression data, will be collected.

4.4.2 Data Collection and Follow-up for Withdrawn Subjects

Patients taken off study due to toxicity will be followed until resolution or stabilization. All patients will be followed for PFS and OS data.

5 Study Drug

5.1 Description

Pembrolizumab is a humanized anti-programmed cell death 1 (anti-PD-1) monoclonal antibody (mAb) of the immunoglobulin G4 (IgG4)/kappa isotype with a stabilizing S228P sequence alteration in the fragment crystallizable (Fc) region. Pembrolizumab binds to human PD-1 and blocks the interaction between PD-1 and its ligands. The theoretical molecular weight of the polypeptide is 146,288 daltons (Da) and its theoretical isoelectric point (pI) is 7.5. The parental murine anti-human PD-1 antibody (hPD-1.09 \AA) was produced by immunizing mice with hPD-1 DNA. The pembrolizumab antibody was generated by humanization of the parental antibody by the Medical Research Council (Cambridge, UK) using complementarity determining region grafting technology (U.S. Patent No. 5,225,539). The gene segments encoding the variable heavy and light chains of pembrolizumab, as well as human IgG4, were codon-optimized, synthesized, and ligated into a vector.

A single expression plasmid, pAPD11V1-GA, was constructed for the expression of both the heavy and light antibody chains of pembrolizumab. The nucleotide sequences encoding the heavy and light chains, along with their respective promoters and poly A signal sequences, have been confirmed by

Phase II Pembrolizumab Reirradiation

DNA sequence analysis. The pAPD11V1-GA expression vector was subsequently used to transfect CHO-DXB-11 cells for the development of the pembrolizumab-producing cell line.

5.2 Treatment Regimen

Patients will be treated with reirradiation with or without standard concurrent chemotherapy to all gross disease with proton beam therapy. The intended radiation dose should be at least 60 Gy of reirradiation in 1.8-2.0 Gy fractions with or without concurrent chemotherapy or in 4.0 Gy fractions without chemotherapy, at the provider's discretion. This corresponds to daily fractionated radiation over a period of approximately 3-8 weeks. The decision to use concurrent chemotherapy, and which regimen to utilize, are left to the discretion of the treating oncologist. The chemotherapy regimen and doses will be recorded in the patient record.

Pembrolizumab will be started 4 to 12 weeks after completion of reirradiation. Pembrolizumab will be given at a dose of 200 mg intravenously approximately every 21 days for 17 cycles (about 12 months) if there is no evidence of progressive disease or intolerable side effects.

Dose Modifications (Escalation/Titration/Other)

Adverse events (both non-serious and serious) associated with pembrolizumab exposure may represent an immunologic etiology. These adverse events may occur shortly after the first dose or several months after the last dose of treatment. Pembrolizumab must be withheld for drug-related toxicities and severe or life-threatening AEs as per 3 below. See Section 5.6 for supportive care guidelines, including use of corticosteroids.

Table 1: Dose Modification Guidelines for Drug-Related Adverse Events

Toxicity	Hold Treatment For Grade	Timing for Restarting Treatment	Treatment Discontinuation
Diarrhea/Colitis	2-3	Toxicity resolves to Grade 0-1	Toxicity does not resolve within 12 weeks of last dose or inability to reduce corticosteroid to 10 mg or less of prednisone or equivalent per day within 12 weeks
	4	Permanently discontinue	Permanently discontinue
AST, ALT, or Increased Bilirubin	2	Toxicity resolves to Grade 0-1	Toxicity does not resolve within 12 weeks of last dose
	3-4	Permanently discontinue (see exception below) ^a	Permanently discontinue
Type 1 diabetes mellitus (if new onset) or Hyperglycemia	T1DM or 3-4	Hold pembrolizumab for new onset Type 1 diabetes mellitus or Grade 3-4 hyperglycemia associated with evidence of beta cell failure	Resume pembrolizumab when patients are clinically and metabolically stable
Hypophysitis	2-4	Toxicity resolves to Grade 0-1. Therapy with pembrolizumab can be continued while endocrine replacement therapy is instituted	Toxicity does not resolve within 12 weeks of last dose or inability to reduce corticosteroid to 10 mg or less of prednisone or equivalent per day within 12 weeks
Hyperthyroidism	3	Toxicity resolves to Grade 0-1	Toxicity does not resolve within 12 weeks of last dose or inability to reduce corticosteroid to 10 mg or less of prednisone or equivalent per day within 12 weeks
	4	Permanently discontinue	Permanently discontinue
Hypothyroidism		Therapy with pembrolizumab can be continued while thyroid replacement therapy is instituted	Therapy with pembrolizumab can be continued while thyroid replacement therapy is instituted
Infusion Reaction	2 ^b	Toxicity resolves to Grade 0-1	Permanently discontinue if toxicity develops despite adequate premedication
	3-4	Permanently discontinue	Permanently discontinue

Phase II Pembrolizumab Reirradiation

Toxicity	Hold Treatment For Grade	Timing for Restarting Treatment	Treatment Discontinuation
Pneumonitis	2	Toxicity resolves to Grade 0-1	Toxicity does not resolve within 12 weeks of last dose or inability to reduce corticosteroid to 10 mg or less of prednisone or equivalent per day within 12 weeks
	3-4	Permanently discontinue	Permanently discontinue
Renal Failure or Nephritis	2	Toxicity resolves to Grade 0-1	Toxicity does not resolve within 12 weeks of last dose or inability to reduce corticosteroid to 10 mg or less of prednisone or equivalent per day within 12 weeks
	3-4	Permanently discontinue	Permanently discontinue
All Other Drug-Related Toxicity ^c	3 or Severe	Toxicity resolves to Grade 0-1	Toxicity does not resolve within 12 weeks of last dose or inability to reduce corticosteroid to 10 mg or less of prednisone or equivalent per day within 12 weeks
	4	Permanently discontinue	Permanently discontinue

Note: Permanently discontinue for any severe or Grade 3 drug-related AE that recurs or any life-threatening event.

^a For patients with liver metastasis who begin treatment with Grade 2 AST or ALT, if AST or ALT increases by greater than or equal to 50% relative to baseline and lasts for at least 1 week then patients should be discontinued.

^b If symptoms resolve within one hour of stopping drug infusion, the infusion may be restarted at 50% of the original infusion rate (e.g., from 100 mL/hr to 50 mL/hr). Otherwise dosing will be held until symptoms resolve and the subject should be premedicated for the next scheduled dose; Refer to Infusion Treatment Guidelines for further management details.

^c Patients with intolerable or persistent Grade 2 drug-related AE may hold study medication at physician discretion. Permanently discontinue study drug for persistent Grade 2 adverse reactions for which treatment with study drug has been held, that do not recover to Grade 0-1 within 12 weeks of the last dose.

Dosing interruptions are permitted in the case of medical / surgical events or logistical reasons not related to study therapy (e.g., elective surgery, unrelated medical events, patient vacation, and/or holidays). Subjects should be placed back on study therapy within 3 weeks of the scheduled interruption, unless otherwise discussed with the Sponsor. The reason for interruption should be documented in the patient's study record.

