 - When symptoms improve to Grade 1 or less, steroid taper should be started and continued over no less than 4 weeks.

Phase II Pembrolizumab Reirradiation

- **Type 1 diabetes mellitus (if new onset, including diabetic ketoacidosis [DKA]) or ≥ Grade 3 Hyperglycemia, if associated with ketosis (ketonuria) or metabolic acidosis (DKA)**
 - For **T1DM** or **Grade 3-4** Hyperglycemia
 - Insulin replacement therapy is recommended for Type 1 diabetes mellitus and for Grade 3-4 hyperglycemia associated with metabolic acidosis or ketonuria.
 - Evaluate patients with serum glucose and a metabolic panel, urine ketones, glycosylated hemoglobin, and C-peptide.
- **Hypophysitis:**
 - For **Grade 2** events, treat with corticosteroids. When symptoms improve to Grade 1 or less, steroid taper should be started and continued over no less than 4 weeks. Replacement of appropriate hormones may be required as the steroid dose is tapered.
 - For **Grade 3-4** events, treat with an initial dose of IV corticosteroids followed by oral corticosteroids. When symptoms improve to Grade 1 or less, steroid taper should be started and continued over no less than 4 weeks. Replacement of appropriate hormones may be required as the steroid dose is tapered.
- **Hyperthyroidism or Hypothyroidism:**

Thyroid disorders can occur at any time during treatment. Monitor patients for changes in thyroid function (at the start of treatment, periodically during treatment, and as indicated based on clinical evaluation) and for clinical signs and symptoms of thyroid disorders.

 - **Grade 2** hyperthyroidism events (and **Grade 2-4** hypothyroidism):
 - In hyperthyroidism, non-selective beta-blockers (e.g. propranolol) are suggested as initial therapy.
 - In hypothyroidism, thyroid hormone replacement therapy, with levothyroxine or liothyroinine, is indicated per standard of care.
 - **Grade 3-4** hyperthyroidism
 - Treat with an initial dose of IV corticosteroid followed by oral corticosteroids. When symptoms improve to Grade 1 or less, steroid taper should be started and continued over no less than 4 weeks. Replacement of appropriate hormones may be required as the steroid dose is tapered.
- **Hepatic:**
 - For **Grade 2** events, monitor liver function tests more frequently until returned to baseline values (consider weekly).
 - Treat with IV or oral corticosteroids
 - For **Grade 3-4** events, treat with intravenous corticosteroids for 24 to 48 hours.

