Grade 3 and Grade 4	Withhold Pembrolizumab Discontinue if unable to reduce corticosteroid dose to < 10 mg per day prednisone equivalent within 12 weeks of toxicity	Systemic corticosteroids are indicated in addition to appropriate symptomatic treatment. May utilize 1 to 2 mg/kg prednisone or equivalent per day. Steroid taper should be considered once symptoms improve to Grade 1 or less and tapered over at least 4 weeks.

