8.2.4 Evaluating Adverse Events

An investigator who is a qualified physician will evaluate all adverse events according to the NCI CTCAE, version 5.0. Any adverse event which changes CTCAE grade over the course of a given episode will have each change of grade recorded on the adverse event case report forms/worksheets. All adverse events regardless of CTCAE grade must also be evaluated for seriousness.

Table 8: Evaluating Adverse Events

An investigator who is a qualified physician, will evaluate all adverse events as to:

V5.0 CTCAE Grading	Grade 1	Mild; asymptomatic or mild symptoms; clinical or diagnostic observations only; intervention not indicated.
	Grade 2	Moderate; minimal, local or noninvasive intervention indicated; limiting age-appropriate instrumental ADL.
	Grade 3	Severe or medically significant but not immediately life-threatening; hospitalization or prolongation of hospitalization indicated; disabling; limiting self-care ADL.
	Grade 4	Life threatening consequences; urgent intervention indicated.
	Grade 5	Death related to AE

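### At Grade 4, the dosing rules disagree for a few immune events: Table 1's note has no exception for its endocrine rows, and Table 4 treats Grade 4 like Grade 3

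*Combined protocol and SAP*

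**What the plan says.** Section 5.2, Table 1, sets dose modification for drug-related adverse events. Its closing note applies to the whole table: "Permanently discontinue for any severe or Grade 3 drug-related AE that recurs or any life-threatening event". Section 8.2.4, Table 8, defines Grade 4 as "Life threatening consequences; urgent intervention indicated".

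Three endocrine rows of Table 1 bear on this:

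- Hypophysitis, Grades 2 to 4: "Toxicity resolves to Grade 0-1. Therapy with pembrolizumab can be continued while endocrine replacement therapy is instituted".
- New type 1 diabetes, or Grade 3-4 hyperglycemia with evidence of beta-cell failure: hold, then "Resume pembrolizumab when patients are clinically and metabolically stable".
- Hypothyroidism, no grade shown in the text as read: "Therapy with pembrolizumab can be continued while thyroid replacement therapy is instituted".

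Table 1 ends with a catch-all row for all other drug-related toxicity. Grade 3 or severe events are held until they resolve to Grade 0-1; Grade 4 is permanent discontinuation.

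Section 5.6.1.1, Table 4, covers immune-related events that the protocol does not detail in another place. It has its own column on withholding or discontinuing pembrolizumab. Its last row covers Grades 3 and 4 together. The drug is withheld, and then: "Discontinue if unable to reduce corticosteroid dose to < 10 mg per day prednisone equivalent within 12 weeks of toxicity".

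**The concern.** An investigator needs one answer to one question: after a Grade 4 drug-related immune event, may this patient receive pembrolizumab again? For a limited set of events the protocol gives two.

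For Grade 4 hypophysitis, or Grade 4 hyperglycemia with beta-cell failure, the patient's own row permits further dosing while the note under the same table forbids it. For a Grade 4 immune event without its own row, Table 1 stops the drug, whereas Table 4 describes a hold whose end depends on the steroid taper. Uveitis is the clearest case, because Section 3.1 lists it among the pre-specified events of clinical interest and Table 1 has no row for it.

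At stake is treatment conduct and the safety of the individual patient. A site that follows one instruction departs from the other.

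**Working it through.** No arithmetic applies. The check sets the rules side by side at Grade 4, taking Grade 4 as life-threatening on the strength of Table 8.

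| Event at Grade 4 | Most specific rule | General rule | Agree? |
|---|---|---|---|
| Diarrhea/colitis, AST/ALT/bilirubin, hyperthyroidism, infusion reaction, pneumonitis, renal failure/nephritis | Table 1 row: stop permanently (hepatic row has a flagged exception) | Table 1 note: stop permanently | Yes |
| Hypophysitis | Table 1 row: hold, then restart, or continue on hormone replacement | Table 1 note: stop permanently | No |
| Type 1 diabetes/hyperglycemia | Table 1 row: hold, then resume when stable | Table 1 note: stop permanently | No |
| Hypothyroidism | Table 1 row: continue on replacement; no grade shown | Table 1 note: stop permanently | Unclear |
| Immune event without its own row (e.g. uveitis) | Table 4: withhold; discontinue if steroids cannot be reduced | Table 1 catch-all row and note: stop permanently | No |

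Count of Table 1 rows at Grade 4: the six in the first line plus the catch-all row stop the drug (6 + 1 = 7); hypophysitis and diabetes/hyperglycemia allow restart (2); hypothyroidism shows no grade (1). Total 7 + 2 + 1 = 10.

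**First conflict: are the endocrine rows a slip, or is the note incomplete?** The rows look deliberate. The hypophysitis row ties continued dosing to hormone replacement. Section 5.6.1 provides for hormone replacement after Grade 3-4 hypophysitis, and for diabetes it says: "Insulin replacement therapy is recommended for Type 1 diabetes mellitus and for Grade 3-4 hyperglycemia associated with metabolic acidosis or ketonuria". It also places Grade 2-4 hypothyroidism under replacement: "In hypothyroidism, thyroid hormone replacement therapy, with levothyroxine or liothyroinine, is indicated per standard of care". That supports the rows without proving the point, since a patient permanently off pembrolizumab would need replacement too. The likelier error is an exception missing from the note. Table 1 does mark an exception where it wants one: the hepatic row carries a flag to a footnote. The endocrine rows carry none.

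**Second conflict: does Table 4's scope sentence remove the overlap?** Table 4 applies to immune events not covered in another place. If Table 1's catch-all row counts as such a place, Table 4's dosing instruction at Grade 4 has no drug-related event left to govern, and only its supportive-care column does any work. If the catch-all row does not count, the two tables point in different directions for the same event.

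**Does anything else supply the rule?**

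- Section 5.6.1 refers the reader to Section 5.2.1 for dose modification. In the text that material is an unnumbered heading under 5.2. The pointer's meaning is plain, but it does not say that Table 1 overrides Table 4.
- Table 8's rechallenge entry requires advance approval before re-exposure after a serious event that the drug may have caused. It makes that approval follow the protocol's dose modification guidelines, so the approver is sent back to the same tables.
- Section 5.6.1.1 also cites an immune-event guidance document as an attached appendix. It is not available here and might contain a rule.

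**The case against.** **A specific row overrides a general note.** This is the ordinary way to read the endocrine rows, and it is probably what was intended. It stands as a guide to intent. It does not stand as a rule in the document: no precedence is stated, and the note is worded to reach any life-threatening event.

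**Table 1 governs dosing and Table 4 governs care.** Section 5.2 sends readers to 5.6 for supportive care, and 5.6.1 sends them back for dose modification. Table 4 is presented as recommendations and a general approach. A site can obey both tables by withholding under Table 4 and then stopping under Table 1. This is a fair reading and it narrows the point. What remains is that Table 4 has its own dosing column and puts Grades 3 and 4 in one row, so someone working from that page sees a conditional stop at Grade 4.

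**Table 4 never authorizes restart.** Correct. A reader might infer that Table 4 permits rechallenge at Grade 4, or that steroid failure is the sole ground for stopping. It says neither. It has no resume wording, unlike Table 5 for Grade 2 pneumonitis. Restart is implied and no more.

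**Other provisions would stop many of these patients.** Section 4.4.1 lists a toxicity delay of more than four weeks beyond schedule as a reason for withdrawal, and Section 5.8 requires discontinuation for unacceptable toxicity. Steroid tapers of at least four weeks follow both Grade 3-4 hypophysitis and Table 4's Grade 3-4 events, so some patients would leave treatment anyway. These provisions turn on delay or judgement and do not say which Grade 4 rule applies.

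**Re-dosing would be seen.** A reader might infer an unmonitored hazard. The documents do not support that: Section 5.6.1.1 requires immediate Sponsor discussion of immune events of Grade 2 or higher, Section 8.2 requires Grade 3 or higher events to reach the DSMC within five business days, and Table 8 requires advance approval of rechallenge in the cases described. Oversight makes the event visible but leaves the rule unsettled.

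**Conclusion.** The point holds as a minor patient-safety inconsistency in operative dosing text, limited to Grade 4 drug-related events.

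1. Table 1's note lacks an exception for hypophysitis and for type 1 diabetes/hyperglycemia. Hypothyroidism may share the gap, but its grade cell is blank in the text as read and an entry may have been lost in extraction.
2. For immune events without their own Table 1 row, Table 4 implies possible restart at Grade 4 where Table 1's catch-all row stops the drug.

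Of the seven events of clinical interest in Section 3.1, hypophysitis and uveitis are touched, at Grade 4 only, and the thyroid item possibly through hypothyroidism. The other four are not.

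A reader might want to convert this into doses gained or lost, or into an effect on the trial's results. Neither is supported. The documents give no frequency for these events, and the length of hold and the withdrawal provisions would decide how many doses any one patient received. No effect on PFS, power or the 41 patients is claimed.

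The conclusion assumes that Table 8's definition makes Grade 4 life-threatening for the purposes of the note, and that the unseen guidance document does not already set precedence.

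**What to change.** (a) Split Table 4's last row. Keep the current text for Grade 3 and set Grade 4 to permanent discontinuation, matching Table 1's catch-all row.

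(b) Add an exception to the Table 1 note: except hypophysitis or type 1 diabetes/hyperglycemia controlled on hormone or insulin replacement, which follow their own rows. Include hypothyroidism if its row is meant to cover Grade 4. If the sponsor does not intend this exception, set Grade 4 in those rows to permanent discontinuation instead.

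Correcting the pointer in Section 5.6.1 from 5.2.1 to Section 5.2, Table 1, is editorial and can go in at the same time.

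Cost: one amendment with one added clause (or the changed endocrine rows), one split row and one cross-reference. Sample size, visits and analysis are unchanged.
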